3.7. General Issues

General descriptive statistics for numeric variables include the number of observed values, the mean, SD, median, minimum, and maximum values. For categorical variables, the number and percentage of subjects with a specific level of the variable will be presented. Percentages will be calculated based on subjects with reported values (i.e., subjects with missing data will not contribute to denominators of percentages). Descriptive statistics and tabular summaries will be presented by treatment group and, as relevant, by vaccination number or other subdivision.

General reporting conventions will include the following:

- The baseline values for any measurement will be the last value obtained prior to receiving the first vaccination at V1.
- Unless decided otherwise during blinded data review, nominal time points will be used for analysis; actual assessment times (e.g., blood draws) will not be used to reclassify the time point at which a measure was taken.
- Study days until the occurrence of a specific event (e.g., an AE start date) will be calculated relative to the date of randomization/1st vaccination (study day 0) as Date of event minus Date of randomization/1st vaccination administration. Unless information on the specific time (hours and minutes) of an event onset and resolution are known, event durations will be calculated as date of event resolution minus date of onset, plus 1 day.
- Other than log-transformations for immunogenicity data, no transformations are planned.
- Unless otherwise noted, percentages will be presented to one decimal place; means will be reported using one more decimal place than the raw data; the number of decimal places for medians, minima and maxima will be the same as for the raw data; SDs and confidence limits will be reported to the same number of decimal places as for the corresponding mean or percentage; and p-values will be rounded to four decimal places.

- All data listings will be sorted by treatment group and subject screening ID.
- Except for TEAEs and REs, and unless determined otherwise based on blind review of data (per Section 3.4), post-randomization data from unscheduled (out of window) visits will be excluded from the summary tables but included in listings.

3.8. Analysis Populations

The following analysis populations will be used when performing statistical analyses:

- **Enrolled Population** includes all screened subjects who provide informed consent, regardless of whether the subject is randomized. This population will be used to account fully for subject disposition, starting with the informed consent.
- **Safety Population** includes all subjects who were randomized, received a study vaccination, and provided post-vaccination safety data. Since all subjects are assessed for REs immediately following injection, the Safety Population will include all treated subjects unless a subject's safety data is unevaluable for some reason. Analyses based on this population will be analyzed according to actual treatment received at V1. This population will serve as the primary analysis population for study disposition, baseline demographics and medical history, as well as safety analyses.
- **The Full Immunogenicity Population (FIP)** includes subjects in the enrolled population who were randomized, received at least one study vaccination, and have post-vaccination immunogenicity measurement(s). Analyses based on the FIP will be performed according to randomized treatment assignment, regardless of any randomization or allocation errors. Results will serve as supportive analyses for the Primary and Secondary PP_IMM Population results (see below).
- **The Primary Per Protocol Immunogenicity Population (PP_IMM)** includes subjects in the FIP who received all 3 study vaccinations (including booster), contribute post-booster immunogenicity measurements, and have no major protocol deviations that are determined to potentially interfere with the immunogenicity assessment. This population (or a relevant subset of subjects contributing OPA results) will be used to assess the primary immunogenicity objective and secondary immunogenicity objectives 1, 2, and 7.
- **The Secondary PP_IMM Population** includes all subjects in the FIP who received both primary series study vaccinations, contribute immunogenicity measurements at 4-weeks post primary series and/or immediately prior to receiving the booster dose, and have no major protocol deviations that are determined to potentially interfere with the immunogenicity assessment. This population (or a relevant subset of subjects contributing OPA results) will be used to assess secondary immunogenicity objectives 3, 4, 5, and 6, as well when performing the planned interim analysis.

Any exclusions from the Primary and Secondary PP_IMM populations (e.g., due to out-of-window study vaccinations or other protocol violations which could potentially interfere with

immune responses or the interpretation of results) will be established in blind review by the PATH Clinical Lead. Populations used for each category of analysis described in subsequent sections of this SAP are summarized in Table 3.

Table 3. Summary of Planned Analyses, by Population

ANALYSIS	ENROLLED	SAFETY	FIP	PRIMARY PP_IMM	SECONDARY PP_IMM
Disposition	✓	✓			
Baseline		✓		✓	
Safety		✓			
Primary Immunogenicity			✓ ¹	✓	
Secondary Immunogenicity objectives 1, 2, and 7			✓ ¹	✓	
Secondary Immunogenicity objectives 3, 4, 5, and 6			✓ ¹		✓

¹ restricted to subjects who contribute immunogenicity results at the relevant visit(s)

3.9. Covariates

Unless otherwise noted, no covariates will be utilized in primary or secondary statistical analyses of immunogenicity, safety, or tolerability. An exploratory analysis of the effect of duration of elapsed time between completion of the primary series and booster vaccination on post-booster responses and booster effect will be performed, and this analysis may control for covariates such as gender and field site. Additional post hoc analyses which explore the effects of covariates on immune responses may also be conducted.

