3. STUDY DESIGN

This is a prospective, single center, randomized, active-controlled, observer-blind, Phase 3 descriptive study in which 660 healthy Gambian pneumococcal conjugate vaccine (PCV)-naïve infants will be randomized 1:1:1 to receive 3 doses of either PNEUMOSIL, Synflorix or Prevenar 13 at 6 weeks, 14 weeks and 9-18 months of age. Standard EPI vaccinations in The Gambia, except Prevenar 13, will be given concomitantly with all 3 doses of study vaccine (except for subjects who receive the 9-month EPI vaccines earlier than the study booster dose due to impact of the COVID-19 pandemic). The study schema is presented in Table 13.

Screening: After parental informed consent is obtained, prospective subjects will be screened to determine eligibility. While informed consent may occur as early as 4 weeks of age, the screening window will be 6 to 8 weeks of age. Randomization will take place only after a subject has satisfied all eligibility criteria, including confirmation of 1) no acute illness that precludes vaccination; 2) a negative rapid diagnostic test (RDT)/blood film for malaria; and 3) normal vital signs. These same criteria will need to be satisfied prior to administration of any subsequent vaccination.

Primary Series Vaccination and Follow up: Subjects (n=660) deemed eligible to participate in the study by the Principal Investigator (PI) will be randomized in a 1:1:1 ratio based on a pre-established randomization scheme, to receive the first dose of either PNEUMOSIL, Synflorix or Prevenar 13 at 6 (+2) weeks of age (V1). Treatment assignment will be stratified by field site. Subjects will return to the clinic at 10 (+2) weeks of age (V2) for Gambian EPI vaccines (except for Prevenar 13), and at 14 (+2) weeks of age (V3) to receive the 2nd primary dose of study vaccine along with EPI vaccines.

Table 13. Study Schema

Groups	N	Visits / Age (wks)					
		V1	V2	V3	V4	V5	V6
		6 (+2)	10 (+2)	14 (+2)	V3+4 (+2)	9-18 (+1) mo	V5+4 (+2)
PNEUMOSIL	220	X, E	E	X, E	B	B, X, E	B
Synflorix	220	X, E	E	X, E	B	B, X, E	B
Prevenar 13	220	X, E	E	X, E	B	B, X, E	B

wks = weeks, mo = months

X = study vaccination, E= EPI vaccines, B = blood sample for immunogenicity testing

A follow-up visit (V4) will take place at 4 (+2) weeks after the second study vaccine administration, during which blood will be collected for immunogenicity assessments.

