12.7. Immunogenicity Analyses

12.7.1.1. Primary Objective

The primary immunogenicity objective is to evaluate serum IgG antibody responses (GMCs) to the 10 serotypes in PNEUMOSIL, alone and in comparison to antibody responses to these serotypes induced by Prevenar 13 and Synflorix at 4 weeks post booster dose. Serum IgG GMCs will be reported by PNEUMOSIL serotype and treatment group, together with 95% CIs. For each serotype, GMC ratios (PNEUMOSIL vs. each comparator) and associated 95% CIs for the GMC ratio will be reported based on log-linear models, with no adjustment for multiple comparisons.

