3.3. Randomization and blinding

After a subject is confirmed to have met all study eligibility requirements, he or she will be randomized in a 1:1:1 allocation ratio based on a pre-established randomization scheme stratified on field site, and receive the first dose of either PNEUMOSIL, Synflorix, or Prevenar 13 at 6 (+2) weeks of age (V1).

The eligible subject will be assigned the next numeric randomization ID for the given field site. Treatment assignments will be communicated to the unblinded dosing nurse via sealed, opaque, numerically numbered envelopes identified by a unique randomization ID. If a subject is given the wrong treatment at V1 due to an allocation error, the same vaccine will be administered at V3 and V5 so long as the error is identified before the timing of the next injection.

Except for staff responsible for preparing and administering study vaccines, performing vaccine accountability, and maintaining the security of the treatment assignments, all study personnel, including the Principal Investigator (PI) and the Sponsor, will remain blinded to subjects'

individual treatment assignments. All CRO personnel will also remain blinded to individual treatment assignments until the last subject completes V6, with the following exceptions: an unblinded monitor, a clinical supplies manager, a statistician implementing the interim analysis of immunogenicity objectives through V4 and any required unblinded analyses for the Data and Safety Monitoring Board (DSMB), and an Executive Secretary for the DSMB (if required). The interim analysis results shared with the Sponsor will include treatment group-level comparisons, but no information which could reveal individual treatment assignments. Unblinding at interim and final analyses will be conducted and documented in accordance with relevant CRO standard operating procedures (SOPs) and documented in the eTMF when the study is complete. Details regarding maintenance of blinding for any DSMB safety analyses are addressed in the separate DSMB Charter.

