3.5. Selection of OPA Specimens

Prior to the interim analysis of primary series immunogenicity data, the PI provided the ratio of subject enrolments per field site expected to be achieved at the completion of the trial. Based on this ratio, the independent statistician selected (based on order of entry into the study, not randomly) the first 27 subjects with evaluable V4 specimens in each treatment group from the Brikama field site, and the first 23 subjects with evaluable V4 specimens in each treatment group from the Bundung site, such that a total of 50 subjects per group were selected for OPA analysis proportional to the enrolment total in each site. Selected subjects who did not complete V5 per protocol were later replaced with new subjects from the same field site and treatment group to contribute V5 and V6 OPA data (with replacements also selected in order of enrolment date, not randomly). If more than 10% of subjects fail to contribute evaluable results at a given visit, then additional subjects may have their specimens analysed to help ensure at least 45/group contribute to each secondary functional antibody analysis timepoint. The PATH Clinical Lead will make this determination in blind review of data once the availability of OPA results has been determined for all selected subjects.

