3.10. Pooling of Sites and Evaluation of Site Differences

Information from the population flow chart, demographics and final disposition tables will be reported by field site to inform potential site differences. No statistical tests for differences in characteristics across field sites or between treatment groups within site will be conducted.

Except for tests of treatment-group differences in safety outcomes, which will be stratified on field site, analyses will be performed on data pooled across field sites. However, potential site-level effects will be assessed in exploratory analyses of treatment-by-site interactions for differences in proportions of subjects with TEAE and differences in the distribution of highest grade of reactogenicity observed within Day 6 of any vaccination. Interactions significant at $\alpha = 0.05$ will be described in the CSR. Site-specific tables summarizing treatment-group differences in key TEAE categories may also be produced, but formal statistical testing of treatment-by-site interactions within such categories will not be conducted. Differences in immunogenicity responses between sites may also be explored (e.g., when assessing log-normality assumptions), but no formal statistical tests of treatment by site interactions will be reported.

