5. EVALUATION OF IMMUNOGENICITY

Analysis Populations: Primary and secondary immunogenicity will be evaluated within the Primary and Secondary Per Protocol Immunogenicity Populations, as noted in Table 3.

Data Sources: Primary immunogenicity objectives will be based on serotype-specific IgG antibody concentrations measured 4 weeks after the booster vaccination series (V6). Secondary objectives will be based on the serotype-specific IgG concentrations and OPA titers at three time points (4-weeks after completion of the primary series (V4), immediately prior to booster (V5), and V6).

Endpoint Definitions:

1. **GMC [or GMT]:** The geometric mean concentration (or titer) = antilog (mean $[\log_{10} x]$), where x is the assay result
2. **Response to study vaccine:**
 - IgG concentration $\geq 0.35 \mu\text{g/mL}$
 - IgG concentration $\geq 1.00 \mu\text{g/mL}$
 - OPA titer ≥ 8

5.1. General Comments on Reporting of Immunogenicity Objectives:

1. Differences in proportions of responders to each serotype in PNEUMOSIL will be reported as the PNEUMOSIL proportion minus the reference group (Synflorix or Prevenar 13) proportion, with 95% confidence intervals calculated using the Miettinen-Nurminen (1985) likelihood score method. If the response rate is 100% in each group, then two non-response records (one for each group) will be included and given a weight of 0.000001 to facilitate computation of the 95% CI. Differences in proportions will be considered statistically significant if the 95% CI excludes 0.
2. Within-group GMCs [GMTs] and 95% CIs for each serotype in PNEUMOSIL will be computed based on the antilog (base 10) of mean log10 concentrations [titers] and the corresponding CI limits for the mean log10 values, based on a log-normality assumption.
3. Between-group GMC [GMT] ratios will be reported as the PNEUMOSIL GMC [GMT] divided by the reference vaccine GMC [GMT]. 95% CIs for between-group GMC [GMT] ratios will be computed based on the antilog (base 10) of the corresponding CI limits for the difference in mean log10 concentrations [titers]. Differences between groups will be considered statistically significant if the 95% CI excludes 1.

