5.2. Analysis of primary immunogenicity endpoint

The Primary immunogenicity objective is to evaluate the serum IgG GMCs to the 10 serotypes in PNEUMOSIL, alone and in comparison to IgG antibody responses to these serotypes induced by Prevenar 13 and Synflorix, at 4 weeks post booster dose. For each serotype, two-sided 95% CIs for the within-group GMC and the between-group GMC ratios will be calculated. Differences between groups will be considered statistically significant if the 95% CI for the GMC ratio excludes 1.0.

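### Between-group GMC and GMT ratios leave out the field-site stratum used in randomisation: a small, conservative loss of precision

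*SAP*

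**What the plan says.** Both documents make field site a design factor. Protocol 3 states: "Treatment assignment will be stratified by field site". SAP 3.3 refers to a "pre-established randomization scheme stratified on field site".

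The immunogenicity comparison does not use it. SAP 3.9 states: "Unless otherwise noted, no covariates will be utilized in primary or secondary statistical analyses of immunogenicity, safety, or tolerability". SAP 3.10 makes one exception, for tests of group "differences in safety outcomes, which will be stratified on field site, analyses will be performed on data pooled across field sites". SAP 5.1 item 3 then says "95% CIs for between-group GMC [GMT] ratios will be computed based on the antilog (base 10) of the corresponding CI limits", the limits being those of the plain difference in mean log10 values. For the primary endpoint, SAP 5.2 adds: "Differences between groups will be considered statistically significant if the 95% CI for the GMC ratio excludes 1.0".

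Protocol 12.7.1.1 says that "associated 95% CIs for the GMC ratio will be reported based on log-linear models" and names no covariates.

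Site does matter elsewhere in the plan. The safety tests are stratified on it (SAP 5.4.2, 5.4.3). SAP 3.9 lists it as a possible covariate in the exploratory analysis of booster timing. The OPA specimens are chosen by site quota: 27 per arm from Brikama and the "first 23 subjects with evaluable V4 specimens in each treatment group from the Bundung site".

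**The concern.** An analysis should normally carry the factors on which the randomisation was stratified. Stratification is meant to balance the sites across arms. If sites differ in antibody level, that balance lowers the true variance of the arm contrast, but a pooled two-group interval still counts the between-site spread as noise. The interval is then wider than the design warrants, and its coverage rises above the nominal 95%.

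The primary GMC ratios, the OPA GMT ratios and the ratios at the secondary time points are all affected. SAP 5.2 labels a difference significant by whether the interval excludes 1.0, so width bears directly on that label. The plan gives no reason for using site in the safety tests and not here.

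**Working it through.** **Inputs.** IgG: CV at most 1.5, and 220 per arm less 10%, so 198 (Protocol 12.1, SAP 3.2.1). VAC-056 CVs ran from 0.89 to 1.46 (same sections). OPA: CV at most 2.11, and 50 per arm less 10%, so 45 (SAP 3.2.3). Site split: 27:23, so p = 0.54; SAP 3.5 sets this quota in proportion to enrolment. The ratio of GMCs between the two sites, g, is not in the documents and is an assumption throughout.

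**Reproducing the plan's figures.** The log SD is sqrt(ln(1 + CV²)), and the interval around a ratio of 1.0 is exp(± t × SD × sqrt(2/n)).
- IgG: SD = sqrt(ln 3.25) = 1.0857. With n = 198 and no site term the interval is 0.807 to 1.239, against the stated 0.81 to 1.24.
- OPA: SD = 1.3023. With n = 45 it is 0.579 to 1.726, against the stated 0.58 to 1.73.

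The stated precision therefore holds without any site adjustment.

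**Effect of a site term.** With total variance held at the planning value, the share due to site is s = p(1−p) × ln(g)² / SD². The log interval narrows by 1 − sqrt(1−s). With arms balanced within site, the unadjusted interval covers 2Φ(1.96/sqrt(1−s)) − 1. The equivalent gain in sample size is n × (1/(1−s) − 1) per arm.

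Example, IgG at g = 1.5: s = 0.2484 × 0.1644 / 1.1787 = 0.0346.

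| Assumed g | s (CV 1.5) | Narrowing, CV 1.5 | Unadjusted coverage, CV 1.5 | Equivalent extra per arm | Narrowing, CV 0.89 | Narrowing, OPA CV 2.11 |
|---|---|---|---|---|---|---|
| 1.25 | 0.0105 | 0.5% | 95.1% | 2.1 | 1.1% | 0.4% |
| 1.5 | 0.0346 | 1.8% | 95.4% | 7.1 | 3.6% | 1.2% |
| 2.0 | 0.1013 | 5.2% | 96.1% | 22.3 | 10.8% | 3.6% |

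For an IgG ratio of 1.0 at CV 1.5, the interval becomes 0.810 to 1.235 at g = 1.5 and 0.816 to 1.226 at g = 2.0. For OPA it becomes 0.583 to 1.714 and 0.591 to 1.692. In the most favourable case examined (CV 0.89, g = 2.0), 0.860 to 1.163 becomes 0.874 to 1.144.

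**Simulation.** With site-balanced arms and 40,000 runs per case at CV 1.5, the adjusted-to-unadjusted width ratios were 1.000, 0.995, 0.982 and 0.948 for g = 1.0, 1.25, 1.5 and 2.0, in line with the formula. Unadjusted coverage was 95.0%, 94.8%, 95.3% and 96.2%. The value at 1.25 is a little below the formula; adjusted coverage in the same runs was also low (94.7%), so I read it as simulation noise.

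**Cost if sites do not differ.** The model loses one degree of freedom. The log interval widens by less than 0.01% for IgG (394 to 393) and by 0.02% for OPA (88 to 87).

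**Proportions.** Stratifying the Miettinen-Nurminen intervals would create sparse cells. With 50 per arm split 27/23, the chance that both arms are at 100% is π^100 pooled, and 1 − (1 − π^54)(1 − π^46) in at least one site. At a true OPA response π of 0.95 this is 0.6% against 15.1%; at 0.98 it is 13.3% against 59.8%.

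**The case against.** The case for leaving the plan alone is respectable.

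- The choice is openly prespecified and consistent across SAP 3.9, 3.10 and 5.1.
- The study is descriptive: Protocol 12.1 specifies no hypothesis tests, and there is no margin or success criterion. The significance label in SAP 5.2 triggers no decision.
- Every figure for the gain depends on an assumed site effect. The field sites are a short distance from Fajara (Protocol 4.1), in one peri-urban coastal region (Protocol 6.1.1), and the assays are run centrally (Protocol 8.1, 8.3). Nothing points to a two-fold site difference.
- A site-adjusted ratio need not equal the quotient of the two GMCs printed beside it, and the response-rate differences would remain unadjusted.
- SAP 3.12 shares V4 group comparisons with the sponsor at the interim, so a later change of estimator for V4 needs explaining.

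Most of this stands, and it sets the priority low. It does not remove the point, because matching the analysis to the randomisation costs next to nothing.

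One further objection is that the over-coverage needs arms balanced within site, and the documents state stratification but no block size. The condition is real and is kept in the verdict. However, at a site ratio of 2.0 unadjusted coverage stays about 96% under site-balanced allocation even with 10% random dropout, and falls only to 95.0% if site is not balanced across arms. In the OPA subset, the quota and the same-site, same-arm replacements (SAP 3.5) maintain balance by design.

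**Conclusion.** The omission is real, and its effect is small and conservative. Given balance within site, the pooled ratios are unbiased and their intervals are at most slightly too wide. At the planning CV of 1.5 the loss is under 2% of log width for site ratios up to 1.5 and about 5% at 2.0. At CV 0.89 it reaches about 11% at 2.0. The documents give no site effect, so the size cannot be bounded from them; that it is small is a judgement.

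A reader might infer more than the documents support:
- **That the primary comparison is biased or the false-positive rate inflated.** With balanced strata the error runs the other way.
- **That the sample size fails.** The stated precision reproduces with no site term.
- **That the SAP contradicts the protocol.** A log-linear model with treatment alone satisfies Protocol 12.7.1.1.
- **That the wider interval tilts the study towards its hypothesis of similar responses (Protocol 2.1).** There is a slight lean, but with no margin and no rule by which similarity is declared, nothing turns on it.

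**What to change.** In SAP 3.9, 3.10 and 5.1 item 3, state that the between-group GMC and GMT ratios (primary objective and secondary objectives 1 and 3 to 6), with their 95% CIs, come from a linear model on log10 values with treatment and field site as fixed factors. Item 3 must be edited too, because it defines the ratio as a simple quotient. Keep the within-group GMCs and GMTs and the unadjusted ratio as supportive results, and note that the adjusted ratio may differ slightly from the quotient of the reported means. State how site enters the bootstrap fallback in SAP 3.14. If V4 interim results have already been shared, say that the change followed them.

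Leave the Miettinen-Nurminen intervals unstratified, for the sparse-cell reason shown above.

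The cost is one model term on a variable already collected, plus the supportive ratios: 6 assay-visit combinations × 10 serotypes × 2 comparators = 120 per analysis population.

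Two editorial points, neither a finding in its own right:
- SAP 5.3.5 and 5.3.6 give the pre-booster age as 9 months, against 9-18 months in SAP 2.1.2 and 3.1 and in the protocol. Both sections tie the analysis to V5, so no estimate changes, but the wording should be reconciled.
- SAP 5.4.2 and 5.4.3 stratify the Cochran-Mantel-Haenszel tests without saying whether the accompanying CIs are stratified. One sentence would settle it.

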	
schedule administered at 9 months of age or later. The updated WHO position paper in 2019 specifies that the booster dose of a 2+1 schedule should be given at 9-18 months of age. Which of the two PCV schedules a country adopts should be based on factors such as the epidemiology of pneumococcal disease in the country and coverage rates for EPI vaccines at 9 months of age or later. Because of the longer duration of protection that a booster dose may provide – particularly against serotypes of concern such as types 1 and 5, an increasing number of countries have adopted a 2+1 schedule in their EPI programmes, including India in 2018.
 
The current Phase 3 descriptive study will provide data necessary to evaluate the safety and immunogenicity of PNEUMOSIL when administered in an alternative schedule to the 3 dose primary schedule (3+0) evaluated in the Phase 3 pivotal trial (VAC-056) – namely in a 2 dose primary and booster (2+1) schedule – and compare immunogenicity to that of both currently licensed second-generation PCVs administered in the same 2+1 schedule. A Phase 3 trial is also being planned to evaluate the safety and immunogenicity of PNEUMOSIL administered in a 2+1 schedule in Indian infants. These studies will support regulatory approval of PNEUMOSIL in countries that have adopted a 2+1 schedule for routine PCV immunization in their EPI programme.
 
The study design has necessarily been modified due to the interruption of field activities related to the Covid-19 pandemic. The planned booster vaccination at 9 months of age has been extended to an age range of 9-18 months. This is consistent with the 2019 WHO position paper. Standard EPI vaccines will be given with the booster dose if not already administered within the routine EPI schedule at the time field activities restart.

STUDY DESIGN	
In this prospective, single center, randomized, active-controlled, observer-blind, Phase 3 descriptive study, 660 healthy Gambian pneumococcal conjugate vaccine (PCV)-naïve infants will be randomized 1:1:1 to receive 3 doses of either PNEUMOSIL, Synflorix or Prevenar 13 at 6 weeks, 14 weeks and 9-18 months of age. Standard EPI vaccinations in The Gambia, except Prevenar 13, will be given concomitantly with all 3 doses of study vaccine (except for subjects who receive the 9-month EPI vaccines earlier than the study booster dose due to impact of the COVID-19 pandemic).

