The broadest possible age range consistent with WHO recommendations for timing of the booster dose in a 2+1 schedule (9-18 months of age) has been adopted in order to manage uncertainty in the study introduced as a result of the COVID-19 pandemic, which necessitated a suspension of study visits (to protect study subjects, their families and study staff from potential exposure to SARS-CoV-2). Given the uncertain date for resumption of study visits, the protocol allows the booster vaccination to be administered at 9-18 months of age, with the plan to complete the booster vaccinations in as expedited a manner as possible once the study is resumed in order to capture as many subjects at 9 months of age as possible. The rationale for prioritizing boosting at 9 months of age is that this age is aligned with the EPI schedule in The Gambia as well as many other low-to-middle income countries, and is commonly the age at which the booster dose of a 2+1 PCV schedule is given in such countries. EPI vaccines will be co-administered with the booster dose of study vaccine, except in the case of subjects who have reached 9 months of age prior to resumption of the study. In these subjects, 9-month EPI vaccines will continue to be administered at 9 months (+1 month window) to the degree it is considered to be reasonable by the PI in country, in discussion with the sponsor. Such decisions will take into account the operations of the routine governmental EPI clinics, the level of SARS-CoV-2 transmission in country and broader guidance on field operations provided by MRCG leadership in line with Government of The Gambia policies.

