5.3.8. Exploratory Analyses of Immunogenicity Data

Due to the impact of the COVID-19 pandemic on clinic visit schedules, a protocol amendment extended the range in which booster vaccinations are given from 9 (+1) months to 9-18 (+1) months of age. The change enables the study to explore the effect of the length of time between completion of the primary series and administration of the booster dose on post-booster responses and booster effects. We will use log-linear models to explore the effect of time between V4 and V5 on post-booster IgG and OPA responses in each treatment group (GMCs and GMTs), and log-linear random effects models to explore the effects of time on booster responses (GMC and GMT ratios). Generalized linear models with logit link will be used to explore the corresponding effects of time on post-booster seroresponse rates (IgG concentrations ≥ 0.35 $\mu\text{g/mL}$; IgG concentrations ≥ 1 $\mu\text{g/mL}$; OPA titer ≥ 8). Analyses will be restricted to the Primary Per Protocol Immunogenicity Population. All results will be reported as exploratory in nature using descriptive 95% CIs and p-values.

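### The exploratory model of booster delay does not name EPI co-administration at V5, although the protocol confines boosting without EPI vaccines mainly to delayed infants

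*SAP*

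**What the plan says.** SAP 5.3.8 sets out the purpose: "The change enables the study to explore the effect of the length of time between completion of the primary series and administration of the booster". The model for IgG and OPA levels is log-linear in the V4-V5 interval, intended to "explore the effect of time between V4 and V5 on post-booster IgG and OPA responses in each treatment group". Random-effects models for booster ratios and logit models for seroresponse follow. No covariate is named there. SAP 3.9 adds that "this analysis may control for covariates such as gender and field site", and then allows further post hoc covariate analyses. On status, SAP 5.3.8 states: "All results will be reported as exploratory in nature using descriptive 95% CIs and p-values".

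The protocol links EPI vaccination at V5 to delay. Section 1.10 has EPI vaccines given with the booster "except in the case of subjects who have reached 9 months of age prior to resumption of the study". For those infants, "9-month EPI vaccines will continue to be administered at 9 months (+1 month window) to the degree it is considered to be reasonable"; that judgement is left to the investigator, with the sponsor consulted. The Protocol Summary (Study Rationale) gives the remaining rule: "Standard EPI vaccines will be given with the booster dose if not already administered within the routine EPI schedule" when field work restarts. Protocol 7.1.2 has the EPI vaccines given at each vaccination visit recorded on the CRF.

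**The concern.** The interval was not randomized. It depends largely on a child's age when the study resumed, and under the protocol the same circumstance decides whether the booster is given with measles-rubella, yellow fever and OPV or without them. Gender and field site, the only covariates named, are not tied to delay by any protocol rule. A slope fitted with those covariates, or with none, therefore cannot separate a longer interval from the absence of co-administered vaccines.

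At stake is the interpretation of the one SAP analysis of what the move to a 9-18 month booster did to the response. It is fitted by serotype and treatment group with unadjusted p-values, and booster timing is a programme question that Protocol 1.10 itself discusses.

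**Working it through.** **1. The plan's own figures.** The documents give no figure for the delay model. SAP 3.2.1 supplies the spread: CV at most 1.5, 220 per group, at most 10% non-evaluable, so 198.
- SD on the natural-log scale = sqrt(ln(1 + 1.5²)) = 1.086.
- 95% CI factor for a GMC = exp(±1.97 × 1.086/√198) = 0.859 to 1.164 (stated 0.86 to 1.16).
- For a GMC ratio of 1, with an extra √2: 0.807 to 1.239 (stated 0.81 to 1.24). The plan's figures reproduce.

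**2. Range of the exposure.** V4 falls at about 14 + 4 = 18 weeks, or 4.1 months. A booster at 9 to 18 months gives an interval of about 4.9 to 13.9 months, a range of 9 months before visit windows.

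**3. Bias formula.** Let g be the GMC ratio of boosting without versus with EPI vaccines, and let the true time effect be zero. The model without the indicator has expected log slope = ln(g) × cov(t, alone)/var(t), where t is delay and alone = 1 if no EPI vaccines were given at V5.

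**4. Assumed inputs (none is in the documents).** A proportion p of infants is delayed, with delay uniform over 1-9 months; the rest are uniform over 0-1 month. A proportion q of delayed infants is boosted alone. Mean delay is 5 months versus 0.5, a difference of 4.5. Then:
- cov = p(1−p) × q × 4.5
- var = p × 64/12 + (1−p)/12 + p(1−p) × 4.5²

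**5. Worked case: p = 0.5, q = 0.5, g = 1.25.**
- cov = 0.25 × 0.5 × 4.5 = 0.5625; var = 2.667 + 0.042 + 5.063 = 7.771.
- Slope = 0.2231 × 0.5625/7.771 = 0.0162 per month. Over 9 months: exp(0.145) = 1.16-fold.
- SE of slope = 1.086/√(198 × 7.771) = 0.0277, so slope/SE = 0.58. The chance of a falsely significant time effect is about 9% per serotype and group, against 5%.

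**6. Range over p = 0.3-0.7 and q = 0.25-1.**

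| Assumed g | Spurious change over 9 months | False-positive rate |
|---|---|---|
| 1.00 | none | 5% |
| 1.10 | 1.03 to 1.15 | about 5-8% |
| 1.25 | 1.06 to 1.38 | about 6-22% |
| 1.50 | 1.11 to 1.79 | about 7-56% |

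A ratio below 1 gives the mirror image on the log scale.

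**7. Cost of adjusting.** Over the same scenarios the correlation of delay with boosting alone is 0.22 to 0.85, so the variance inflation 1/(1 − r²) is 1.05 to 3.6. With p = 0.5:
- IgG: the 95% CI factor for a 9-month change is exp(1.96 × 9 × 0.0277) = 1.63 either way without the indicator; 1.74 with it at q = 0.5 (inflation 1.28); 2.29 at q = 1 (inflation 2.87).
- OPA (CV 2.11, log SD 1.302, 45 evaluable of 50): SE = 1.302/√(45 × 7.771) = 0.0696. The corresponding factors are 3.4, 4.0 and 8.0.

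**The case against.** **The SAP does not forbid the term.** The covariate list is optional and open, and post hoc analyses are allowed. That is right: the gap is that the indicator is not named in advance, not that the SAP excludes it. Leaving it unnamed does allow the choice to be made after results are seen.

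**The harm is hypothetical.** Nothing in the documents shows that these EPI vaccines alter the pneumococcal booster response. The VAC-056 results in Protocol 1.8.2 compare EPI responses between pneumococcal vaccine groups, which is the reverse question. This stands, and the point is conditional on it.

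**Co-administration may be a consequence of delay.** On that view the unadjusted slope is the total effect of late boosting as it happened in this trial, and adjustment answers a different question. That is a fair estimand point. Reporting both slopes meets it.

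**Stronger readings the documents do not support.**
- A reader might infer that co-administration falls from nearly all to nearly none across the range, so that its whole effect is credited to time. But delayed infants who missed the EPI visit still get those vaccines with the booster, their share is not given, and the 18-month EPI vaccines (Protocol Table 12) could coincide with the latest boosters.
- A reader might take co-administration to be the only factor tied to delay. Age at booster follows the V4-V5 interval almost exactly, because V4 falls at a nearly fixed age.
- A reader might expect a fit among infants boosted alone to be free of confounding. Their EPI vaccines were scheduled at 9 (+1) months, so time since EPI vaccination rises with delay.

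**Conclusion.** The point holds as a modest, conditional one. Boosting without EPI vaccines is tied by protocol to delay, it is recorded, and the SAP does not name it in the only model of delay. If it affects the response, the time slope partly reflects it. How much is unknown: the ranges in the table rest on assumed values for the proportion delayed, the share boosted alone and the effect itself, and the bias is zero if that effect is absent. Even after adjustment the slope is not a pure interval effect, because age at booster remains inseparable from it.

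It would be wrong to infer a threat to the trial's main results. This analysis is labelled exploratory, and the primary and secondary comparisons between randomized groups are unaffected.

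**What to change.** In SAP 3.9 and 5.3.8:
- Name an indicator of EPI vaccination at V5, taken from the CRF, that records which vaccines were given, so that 18-month EPI vaccines are distinguished from 9-month ones.
- Report the time effect from the log-linear, random-effects and logit models with and without it.
- Tabulate co-administration by length of delay, so the reader can see how far the two overlap.
- Describe the result as an association with delay that cannot be separated from age at booster.
- Add a fit restricted to infants boosted without EPI vaccines as a sensitivity analysis only.

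The cost is one model term, one table and one subset fit on data already collected. The statistical price is a wider interval for the time effect. This is tolerable for IgG in most of the scenarios above but possibly uninformative for OPA, with about 50 infants per group.
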